8.2. Serious adverse events (SAEs)

8.2.1. Definition of SAEs

SAEs refer to medical events that occur during the clinical study, leading to hospitalization or prolongation of hospital stay, disability, impairment of work capacity, life-threatening condition, death, or congenital malformations, including the following unexpected medical events:

- Events leading to death;
- Life-threatening events (defined as a situation where the subject is at immediate risk of death when the event occurs);

- Events requiring hospitalization or prolongation of hospitalization;
- Events that can lead to permanent or significant disability/incapacity/impairment of work;
- Congenital anomaly or birth defect;
- Other significant medical events (refer to events that are not immediately life-threatening, leading to death or hospitalization, but may jeopardize the subject or require medical or surgical intervention to prevent one of the other outcomes listed in the definition above). Examples of these events include, but are not limited to, the following: allergic bronchospasm requiring intensified treatment in the emergency room or at home, blood dyscrasias or convulsions that do not result in hospitalization, potential drug-induced liver injury, suspected transmission of pathogens (such as pathogenic or non-pathogenic pathogens) through the study drug, pregnancy, drug overdose, secondary tumors, and so on.

8.2.2. Hospitalization

In clinical studies, AEs leading to hospitalization or prolongation of hospitalization should be considered as SAEs. Hospitalization does not include the stay in rehabilitation institutions, nursing homes, routine emergency rooms, or for day surgery (such as outpatient/day/ambulatory surgeries). Any hospitalization or prolongation of hospitalization unrelated to the worsening of AEs is not considered as an SAE. For example:

- Hospitalization due to a pre-existing disease without a new AE or exacerbation of the pre-existing disease (such as hospitalization to check for laboratory abnormalities that occurred prior to the study and are still present);

- Hospitalization for administrative reasons (e.g., annual routine physical examination);
- On-study hospitalization as specified in the protocol (e.g., protocol-specified procedures);
- Elective hospitalization unrelated to the worsening of AEs (e.g., elective surgery);
- Pre-scheduled treatment or surgery which should be documented in the study protocol and/or the subject's baseline data;
- Hospitalization for blood product use only.

Any invasive procedures (such as surgery) and non-invasive procedures for diagnosis or treatment should not be reported as an AE. However, if the medical condition leading to the procedure meets the definition of an AE, it should be reported as an AE. For example, acute appendicitis occurring during the AE reporting period should be reported as an AE, while the appendectomy performed as a result should be documented as the treatment of the AE.

8.2.3. Disease progression

Disease progression is defined as the worsening of the patient's condition caused by the investigational drug targeting the primary tumor, including radiographic progression and the progression of clinical symptoms and signs. The emergence of new metastatic lesions relative to the primary tumor, or the progression of existing metastatic lesions, are considered as disease progression. It will be not reported as an SAE for the events that are life-threatening due to the symptoms and signs of disease progression, requiring hospitalization or prolongation of hospitalization, or lead to permanent or serious disability/incapacity/impairment of work capacity, congenital anomaly, or birth defect. It will be reported as an SAE for deaths caused by symptoms

and signs of disease progression.

8.2.4. Other anti-tumor therapies

SAEs will be recorded from the signing of the ICF until 90 days after the last dose of the investigational drug. If the subject starts a new anti-tumor treatment, follow-up will be conducted until the initiation of the anti-tumor treatment (if it starts within 30 days after the last administration, follow-up will be conducted until at least 30 days after the last administration of SHR-1210; if it starts after 30 days, follow-up will be conducted until the initiation of the anti-tumor treatment). If death occurs within the SAE reporting period after the end of the study treatment, it must be reported regardless of whether the patient has received other treatments.

8.2.5. Follow-up of AEs / SAEs

All AEs/SAEs should be followed up until disappearance, alleviation to baseline level or \leq grade 1, reaching a stable state, or obtaining a reasonable explanation (such as lost to follow-up, death).

The investigator should inquire about any AEs or SAEs that occurred since the last visit at each visit, and provide follow-up information promptly according to the sponsor's query requirements.

8.3. Infusion reactions

Investigators need to closely monitor the possible infusion-related and/or allergic reactions, especially acute immune-mediated adverse reactions (including cytokine storms), throughout the study.

In general, prophylaxis is not required before the infusion of SHR-1210. Based on the published literature, allergic reactions/events are most likely to occur within 24 hours of infusion. If this occurs, the infusion should be slowed down or interrupted according to the situation, clinical supportive treatment should be provided, and

prophylactic medication should be administered before future treatments. Possible allergic reactions may manifest as fever, cold intolerance, chills, headache, rash, pruritus, joint pain, hypotension/hypertension, or bronchospasm. All grade 3 or 4 infusion reactions should be reported according to the SAE reporting procedures.

9. Recommendations for Management of Adverse Events

9.1. Immune-related adverse events (irAEs)

irAEs are clinically significant side effects that are consistent with the immunological mechanism of the drug. Further serological, immunological, and pathological (biopsy) data are required to support their diagnosis. At the same time, other potential causes, such as tumor, infection, metabolism, and toxin, must be ruled out.

Principles for handling irAEs (see Appendix IV for details):

The management of immune-related adverse reactions should be carried out according to the medical practices and guidelines of the study site. The following are treatment recommendations for immune-related adverse reactions for reference.

Patients treated with hormones should be given calcium and vitamin D3 supplementation, acid suppression, and gastric mucosal protection therapy.

- **Immune-related pneumonia**

In the clinical studies of SHR-1210, the monitoring of signs and symptoms of immune-related pneumonia will be strengthened in patients, such as cough and chest discomfort. Chest CT scans will be performed for examination, and high-dose hormonal therapy will be given to patients with \geq grade 2 immune-related pneumonia. Treatment with SHR-1210 may be suspended for patients with grade 2 immune-related pneumonia, while patients experiencing grade 3 or 4 will permanently discontinue SHR-1210. A consultation with a pulmonologist is recommended. Please refer to the following suggestions for specific procedures:

Grade 2 pneumonia: 1 mg/kg/day of methylprednisolone is administered intravenously or orally at an equivalent dose. Closely monitor CT changes and, once the event recovers to grade 1, 0.5 mg/kg/day of prednisone is administered orally for 2 weeks. Subsequently, reduce the prednisone dose by 5 mg per week until discontinuation.

Grade 3 pneumonia: 2 ~ 4 mg/kg/day methylprednisolone is administered intravenously or orally at an equivalent dose. Closely monitor CT changes, once the event recovers to grade 1, reduce the dose by 50% every 3 days and administer 0.5 mg/kg/day of prednisone orally for 2 weeks, then reduce the prednisone dose by 5 mg per week until discontinuation.

If there is no improvement or worsening within 3 ~ 5 days of hormonal therapy, the investigator may communicate with the sponsor to consider the combined use of immunosuppressive agents for treatment.

- **Immune-related hepatitis**

In the clinical studies of SHR-1210, the monitoring of signs and symptoms of immune-related hepatitis will be strengthened in patients, such as liver discomfort and abnormal transaminases increased. High-dose hormonal therapy will be given to patients with \geq grade 2 immune-related hepatitis. Please refer to the following suggestions for specific procedures:

Grade 2 hepatitis: 0.5 ~ 1 mg/kg/day of methylprednisolone is administered intravenously or orally at an equivalent dose. Closely monitor changes in liver function indicators, once the event recovers to grade 1, gradually reduce the hormone dose over a period of no less than one month.

Grade 3 hepatitis: 1 ~ 2 mg/kg/day of methylprednisolone is administered intravenously or orally at an equivalent dose. Closely monitor changes in liver

function indicators, once the event recovers to grade 1, gradually reduce the hormone dose over a period of no less than one month.

If there is no improvement or worsening within 3 ~ 5 days of hormonal therapy, the investigator may communicate with the sponsor to consider the combined use of immunosuppressive agents for treatment.

- **Immune-related enteritis**

In the clinical studies of SHR-1210, the monitoring of signs and symptoms of immune-related enteritis will be strengthened in patients, such as abdominal pain, diarrhea, and hematochezia. High-dose hormonal therapy will be given to patients with \geq grade 2 immune-related enteritis. Patients with grade 2 or 3 immune-related enteritis may temporarily discontinue SHR-1210 and receive treatment, while those with grade 4 will permanently discontinue SHR-1210.

- **Immune-related thyroid dysfunction**

Abnormal thyroid function can occur at any time during the study; therefore, in the studies of SHR-1210, patients' thyroid function will be regularly monitored and special attention will be paid to the clinical symptoms of abnormal thyroid function. Patients with immune-related hyperthyroidism will be treated with high-dose cortisone/prednisone. Hormone replacement therapy will be used for treatment of hypothyroidism, but glucocorticoids are not applicable.

In the clinical studies of SHR-1210, the monitoring of signs and symptoms of immune-related thyroid dysfunction will be strengthened in patients. High-dose hormonal therapy will be given to patients with \geq grade 3 immune-related thyroid dysfunction, and those with grade 4 immune-related thyroid dysfunction will permanently discontinue SHR-1210.

- **Immune-related nephritis and renal failure**

In the clinical studies of SHR-1210, the monitoring of signs and symptoms of immune-related nephritis will be strengthened in patients. For patients with \geq grade 2 immune-related nephritis, high-dose hormonal therapy will be given. Patients with grade 2 immune-related nephritis may temporarily discontinue SHR-1210 and receive treatment, while patients with grade 3 or 4 immune-related nephritis will permanently discontinue SHR-1210.

- **Immune-related hypophysitis**

In the clinical studies of SHR-1210, the monitoring of signs and symptoms of immune-related hypophysitis will be strengthened in patients. For patients with \geq grade 2 immune-related hypophysitis, high-dose hormonal therapy will be given. Treatment with SHR-1210 may be suspended for patients with grade 2 and 3 immune-related hypophysitis, while patients with grade 4 immune-related hypophysitis will permanently discontinue SHR-1210.

- **Other immune-related adverse reactions**

In principle, based on the severity of adverse reactions, the primary action is to suspend SHR-1210. When the severity of the adverse event recovers to \leq grade 1, the re-administration of SHR-1210 can be considered. If a severe grade 3 or life-threatening grade 4 adverse reaction occurs, SHR-1210 will be permanently discontinued

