Concomitant Medications and Therapies	
During the study, the investigator is allowed to provide appropriate supportive therapy based on the clinical needs of subjects. the following Specific medications can be found in the following description of concomitant medications. The use of anti-tumor treatments not specified in the study protocol is prohibited during the treatment, except

	
for medical interventions taken for life-threatening tumor emergencies.
 
1. Permitted concomitant medications
● All concomitant medications/treatments must be recorded in the case report form (CRF), including all prescriptions, over-the-counter drugs, traditional Chinese herbal medicines, intravenous medications, and fluids.● If changes occur during the study, the drug dose, frequency, mode and date of administration should also be recorded in the CRF.2. All concomitant medications/treatments must be recorded between 30 days before the first administration of the investigational drug and 30 days after the last administration in the study.3. Prohibited concomitant medications 
During the screening and treatment periods of the study, subjects are prohibited from receiving the following treatments:
 
● Systemic anti-tumor chemotherapy or biotherapy● Immunotherapy not specified in this protocol● Investigational drugs other than SHR-1210 and apatinib mesylate tablets● Vaccination within 4 weeks prior to treatment administration and during the administration period. Examples of vaccines include, but are not limited to: measles, mumps, rubella, varicella, yellow fever, rabies, Bacillus of Calmette and Guérin, and typhoid (oral) vaccines.
--	---

	
 ● Use of any glucocorticoids other than the treatment of AEs caused by immunotherapy and anti-angiogenic therapy (Note: The physiological doses of steroids may be permitted after communication with the sponsor).
--	---

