4.2. Exclusion criteria

Patients with any of the following conditions will be excluded from the study:

1. Patients who have any active autoimmune diseases or a history of autoimmune diseases (including, but not limited to: autoimmune hepatitis, interstitial pneumonia, uveitis, enteritis, hepatitis, hypophysitis, vasculitis, nephritis, hyperthyroidism, vitiligo, asthma (patients with asthma that has completely

-
- resolved in childhood and requires no any medical intervention in adulthood can be included; patients with asthma requiring medical intervention with bronchodilators cannot be included);
2. Patients who are receiving immunosuppressive agents or systemic hormonal therapy for immunosuppression (at doses > 10 mg/day prednisone or other equivalent hormonal therapy) and are still on treatment within 2 weeks prior to enrollment;
 3. Severe allergic reactions to other monoclonal antibodies;
 4. Patients with hypertension that cannot be well controlled with antihypertensives (systolic blood pressure \geq 140 mmHg or diastolic blood pressure \geq 90 mmHg);
 5. Uncontrolled clinical symptoms or disease of the heart, such as:
 - New York Heart Association (NYHA) grade 2 or higher heart failure
 - Unstable angina
 - Myocardial infarction within 1 year
 - Clinically significant supraventricular or ventricular arrhythmias requiring treatment or intervention
 - QTc > 450 ms (male); QTc > 470 ms (female);
 6. Abnormal coagulation function (international normalized ratio [INR] > 2.0, prothrombin time [PT] > 16 s), with a bleeding tendency or currently receiving thrombolytic or anticoagulant therapy (the prophylactic use of low-dose aspirin and low molecular weight heparin is allowed);
 7. Within 3 months prior to enrollment, subjects with significant clinically relevant bleeding symptoms or a clear bleeding tendency, such as hemoptysis (\geq 2.5 mL/day), gastrointestinal bleeding, esophageal and gastric varices with a risk of bleeding, hemorrhagic gastric ulcers, or vasculitis. If fecal occult blood is

positive at baseline, it can be retested. If it remains positive after retesting, a gastroscopy is required. Patients with severe esophageal and gastric varices indicated by gastroscopy cannot be enrolled (except for those who have undergone gastroscopy within 3 months prior to enrollment to exclude such conditions);

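### Protocol section 9.1 rules out glucocorticoids for hypothyroidism, then orders high-dose hormonal therapy for all thyroid dysfunction of grade 3 or higher, with no exception for hypothyroidism

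*Protocol*

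**What the plan says.** The immune-related thyroid dysfunction entry in Protocol section 9.1 has two paragraphs.

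- The first divides patients by type of disorder. Hyperthyroidism is treated with high-dose cortisone or prednisone. For the opposite disorder it says: "Hormone replacement therapy will be used for treatment of hypothyroidism, but glucocorticoids are not applicable". Neither instruction carries a grade limit.
- The second divides patients by grade. It says that monitoring for "immune-related thyroid dysfunction will be strengthened in patients. High-dose hormonal therapy will be given to patients with" grade 3 or higher disease, and continues "grade 3 immune-related thyroid dysfunction, and those with grade 4 immune-related thyroid dysfunction will" stop SHR-1210 permanently. It does not mention hyperthyroidism or hypothyroidism and does not refer back to the first paragraph.

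Two statements at the head of section 9.1 set the standing of this text. One defers to site practice and guidelines and adds: "The following are treatment recommendations for immune-related adverse reactions for reference". The other is a cross-reference: "Principles for handling irAEs (see Appendix IV for details".

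**The concern.** A patient with immune-related hypothyroidism of grade 3 or higher meets the condition of both paragraphs. If high-dose hormonal therapy means glucocorticoids, the first paragraph withholds them and the second gives them. A clinician who looks up the grade and follows that sentence would give high-dose steroids for a condition for which the same entry says they have no place.

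The situation is foreseeable. Section 6.2 tests thyroid function every cycle from Cycle 2. Section 9.4, under fatigue and weakness, notes that angiogenesis-targeting drugs may cause hypothyroidism, and apatinib is such a drug. Section 10.5.4 lists thyroid dysfunction among the immune-related categories to be summarised. The stake is safety management, not the efficacy result.

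**Working it through.** No arithmetic applies: the point depends on no rate, error level or sample size. The check compares the texts in three steps.

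**1. Do the two rules overlap?**

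| Rule | Type of disorder | Grade | Instruction |
|---|---|---|---|
| First paragraph | hypothyroidism | any | hormone replacement, no glucocorticoids |
| Second paragraph | any thyroid dysfunction | 3 or higher | high-dose hormonal therapy |

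The overlap is hypothyroidism of grade 3 or higher. Neither row exempts it.

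**2. Does hormonal therapy mean glucocorticoids here?** The thyroid entry does not define the term, so the protocol's usage has to decide.

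- The pneumonia and hepatitis entries of section 9.1 also call for high-dose hormonal therapy and then name the drug. For hepatitis: "Grade 3 hepatitis: 1 ~ 2 mg/kg/day of methylprednisolone is administered". The pneumonia entry likewise names methylprednisolone, followed by prednisone.
- Exclusion criterion 2 in section 4.2 refers to doses above "10 mg/day prednisone or other equivalent hormonal therapy".
- Section 9.1 asks for calcium, vitamin D3, acid suppression and gastric protection in patients treated with hormones. That is supportive care for steroid treatment.
- Thyroid replacement has its own term, hormone replacement therapy, in the first paragraph.
- One use is less clear. Exclusion criterion 11 lists hormonal therapy among prior treatments, but it names no drug and does not concern immune-related events.

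On this evidence the second paragraph prescribes glucocorticoids, and the two instructions are opposite in the overlap.

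**3. Does other text resolve it?**

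- The synopsis list of prohibited medications bars "Use of any glucocorticoids other than the treatment of AEs caused by immunotherapy and anti-angiogenic therapy". Steroids for immune-related events are thus permitted, with no thyroid exception, so this rule would not stop the error.
- Table 1 in section 5.3 has no thyroid row. Its general row for other nonhematologic toxicities interrupts both drugs at grade 3, but it concerns study-drug dosing and not steroid treatment. The same is true of the suspension and discontinuation rules in the text of section 5.3.
- Appendix IV is not in the text at hand and could not be checked.

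**The case against.** The strongest reply is that the entry can be read without conflict. The hypothyroidism sentence is specific and unqualified and stands one paragraph earlier, so it can be taken to limit the general grade sentence. Section 9.1 is also not binding: site practice governs, so neither sentence compels treatment at this single center. And Appendix IV may already draw the distinction.

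Much of this stands, and it keeps the point small. It does not remove the contradiction. The protocol states no order of precedence, and the later sentence is worded as an instruction. The harmonising reading also leaves the second paragraph with little to do: hyperthyroidism already receives high-dose steroids at any grade under the first paragraph, so a grade 3 threshold confined to it would either add nothing or silently narrow that rule. A reader asking what the second paragraph adds could reasonably apply it to hypothyroidism. Reference text should still give one answer for one condition.

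It is also fair to say that exempting hypothyroidism makes the mismatch with the ungraded hyperthyroidism sentence more visible. That mismatch is already in the entry; the exemption does not create it.

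**Conclusion.** The concern holds. As written, section 9.1 gives opposite steroid instructions for immune-related hypothyroidism of grade 3 or higher.

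The weight is low: a minor inconsistency in safety guidance, worth correcting at the next amendment. ORR, its Clopper-Pearson interval and the sample size of 30 are untouched. The entry states no glucocorticoid dose and the protocol gives no incidence for this event, so no dose difference or number of patients can be stated.

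The conclusion assumes that hormonal therapy in the grade sentence carries the glucocorticoid meaning it has in the neighbouring entries. Whether the full protocol leaves the point open depends on Appendix IV.

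**What to change.** Replace the treatment part of the grade sentence with wording such as: *Immune-related thyroid dysfunction of grade 3 or higher, other than hypothyroidism, is treated with high-dose glucocorticoids. Hypothyroidism of any grade is treated with thyroid hormone replacement and without glucocorticoids, unless another immune-related event such as hypophysitis calls for them.*

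The last clause preserves the hypophysitis entry, which prescribes high-dose hormonal therapy from grade 2. Leave the grade 4 discontinuation rule as it is, and check Appendix IV for the same wording. The cost is a short wording change at the next amendment and that check, with no extra tests, visits or patients.

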9.2. Handling and reporting of serious adverse events (SAEs)

1) When a SAE is considered, the principal investigator or other responsible physicians should be notified by the attending physician. If the patient's condition is severe, the project leader should be informed while simultaneously providing emergency treatment. If necessary, discontinue the investigational drug immediately.

- 2) If a SAE is judged, based on the clinical manifestations, appropriate treatment or rescue measures should be taken immediately according to the standards of tumor specialty clinical rescue treatment. If the severe toxicity is caused by drug overdose, the investigator will decide to take rescue measures such as accelerating drug excretion to maintain the stability of patient's vital signs as far as possible. If necessary, ECG monitoring should be performed, and consultations and assistance from relevant departments can be requested if needed.
- 3) When an out-of-hospital subject is judged to have a SAE and is unable to visit the clinic, it is recommended that the subject returns to the hospital or seeks medical attention at a local hospital promptly, while immediately notifying the project leader to obtain further advice. If the subject seeks medical attention at a local hospital, establish contact with the attending physician to understand the specific situation and provide treatment recommendations. If necessary, go to the local hospital for treatment or transfer back to the study site for treatment.
- 4) The project leader must report any SAEs in writing within 24 hours to the following parties: the principal investigator, the ethics committee of study site, the sponsor, the SAE specialist at the GCP center, and then the GCP center office will report to the State Food and Drug Administration (SFDA) and the provincial food and drug administration. The content of reporting the serious adverse reaction can use the standard forms provided by the sponsor or the SFDA. The sponsor's reporting should ensure compliance with all reporting procedures required by laws and regulations.
- 5) The study doctor should maintain accurate records of AEs, which should include at least: description of the AE, onset time, the time of resolution, severity and frequency, whether treatment is required, and if so, the treatment provided.
- 6) In the original case report, the occurrence, development, and treatment of the SAE

should be recorded in as much detail as possible and documented in the CRF. The SAE should be followed up until it is properly resolved, the condition is stable, or the cause is clear. In addition, the principal investigator of the study at the GCP center, the ethics committee of the study site, the sponsor, the National Medical Products Administration, and other relevant parties should be provided with the final report (in written form if necessary for some departments).

